- 18. REDCap will send weekly reminders to subjects concerning when to start self-treatment A, when to start self-treatment B. Treatment group A, 'TRE then Fasting', has a low sugar diet and a 10-12 hour eating window. Treatment group B, 'Fasting then TRE', will have an 8 hour eating window with either a 36 or 60 hour water fast once a week.
- 19. FIRST FAST Subjects will be called after they complete the appropriate survey before their first water fast by a medical student volunteer or [name]. They will be informed of what to expect and reminded to take electrolytes. They will be reminded that they can STOP FASTING at any time. They will also be reminded of how to use the symptom flare-up form (via a public link) to talk to a med student and potentially have [name] call them. Per the new **First Fast Call Medical Student Instructions**, the medical student volunteers are expected to talk with subjects within 24 hours of receipt of a First Fast

email notification. Meanwhile, subjects are instructed not to start their first fast until after they have received their Pre-First Fast Call. If the medical student does not reach the subject, they leave a message with their cell phone number. They then must make at least two call attempts by 4 PST the day after the First Fast Call notification was received. All call attempts and their result will be documented in the subject's First Fast Call for m. As a backup, per the crossover emails, if the participant needs to start their first fast but has not been able to talk with a medical student by 7 pm EST, they may call [name]. [name] will check that the subject is indeed correct to initiate their fast at this time. He will then review the Fasting Safety procedures and update the First Fast Call instrument.

- 20. Survey reminders will be sent using the dateDiff function comparing today's date:time to the survey date of each participant's first Baseline Survey. If a subject misses a key survey, then they are considered withdrawn from the study. The first and third baseline surveys, the survey at the end of 4 weeks water fasting and the survey at the end of the relaxed time-restricted eating are considered key surveys.
- 21. If a subject wants to be removed from the study or no longer qualifies from the study, the subject will be removed, but the record will be maintained.

22.

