With successful completion of the 10 week study, participants will be sent a "Participant Completion" email offering a 30-45 min Study Review conference with an investigator. As an attachment, subjects will get a summary of their participation in the study. It will include their weekly Long Covid Symptom Survey scores and subject comments. Also included in the "Participant Completion" email will be language asking the subject to not share their study Long Covid Symptom Survey scores on social media. The letter will also request that subjects not share the study flier on social media - as recruiting for the study must be done only via investigator posts of the flier on social media.

23. If a subject schedules a Study Review conference, at that time, a participant's results, comments, and adherence to the study procedures will be reviewed. The investigator will again remind the subject to not share their study scores and to not share the study flyer on social media.

Safety Procedures

- 23. During water fasts, subjects are asked to drink salt water for electrolytes twice daily. The recipe has Sodium, Potassium and Magnesium in the proper ratios to replace what would normally be obtained from food. This minimizes the risk of refeeding syndrome (which is already a low risk for short water fasts). ½ tsp Morton Lite Salt in 12 ounces of water. In addition, participants are instructed to take a 200 mg Magnesium Glycinate tablet.
- 24. If experiencing severe symptoms, they are to fill out the Symptom Flare-up form via the link in their Participant instructions. Their symptoms will be immediately shared with two 3rd year medical students via an automated REDCap e-mail. The form also provides subjects with the medical student's names and phone numbers. They will try to provide 24-hour support for study subjects. When a medical student identifies a safety concern, they will be referred to [name]. [name] will recommend if the subject should contact 911 emergency immediately and/or be removed from the study. [name] will then report the removal of the subject.

25.

As subjects complete their weekly Symptom Surveys, REDCap notifications will check for self-reported Serious and Concerning Adverse Events.[name], [name] and [name] will be sent all Adverse Event notifications as they are reported. The Investigator or Co-Investigator will create an Adverse Event instrument in REDCap within 24 hours. They will also contact the subject if additional

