2.0 Study Population

The trial population consists of 58 individuals, including 29 randomized to 4 weeks of once-per-week 23-60 hour water-only fasting plus daily 8-hour TRE (16-hour daily water fasting) and a low-sugar diet followed by 4 weeks of 10- to 12-hour daily TRE (daily 12- to 14-hour water-only fasting) and a low-sugar diet, and the other 29 randomized to 4 weeks of daily 10-12 hour TRE (daily 12- to 14-hour water-only fasting) and a low-sugar diet followed by 4 weeks of once-per-week 23-60 hour fasting plus daily 8-hour TRE (16-hour daily water fasting) and a low-sugar diet. All participants engaged in 10 weeks of the study protocol, including a 2-week run-in period of daily 10- to 12-hour TRE (daily 12- to 14-hour water-only fasting) and a low-sugar diet.

- 1.1 Inclusion Criteria: participants must be adults, 18 to 69 years of age; they must have 5 or more of the 28 common Long COVID symptoms, they must reside in the United States of America, and they must be willing to stop the consumption of any nutritional supplements that may activate autophagy.
- 2.1 Exclusion Criteria: At baseline, participants could not have a body mass index below 20 kg/m², could not be pregnant or breastfeeding, and could not have had a SARS-CoV-2 infection within 45 days. Further, they could not carry a diagnosis of type 1 or type 2 diabetes and could not have a history of any eating disorder.
- 3.1 Data Acquisition: All participant data were collected through pragmatic electronic means in REDCap. Weekly symptom and adherence data were collected through similar REDCap forms. All data were stored in REDCap until the end of the study enrollment and follow-up period was complete for all trial participants.

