3.1 Analysis Plan

- 3.1.5 The study population will be evaluated using an intent-to-treat approach to the statistical analysis. All subjects who have data regarding symptom severity scores available at each time point will be included in the analyses.
- 3.2.5 Demographics, anthropometric variables, risk factors, COVID-19 vaccinations, other medications, and socioeconomic variables will be described as percentages or means with standard deviations.
- 3.3.5 Symptom severity scores will be compared between the two study arms using the two-sided paired T-test at each time point, as appropriate. Based on the randomized design of the study, it is expected that most if not all of these data elements will be balanced between the TRE arm and the Fasting arm of the study. Similar comparisons will also be performed to compare between the treatment arms for changes at weeks 1, 2, or 3 of each treatment to examine potential timing of the impact of those interventions.
- 3.4.5 The presence of individual symptoms at baseline, end of the run-in period, end of Fasting, end of TRE, and end of the 10-week trial will be summarized with percentages or means. Examination of overall changes in all participants for LC-score and numLCsym will use two-sided Student's T-test to evaluate the differences in means at baseline and the end of the 2-week run-in phase, and at baseline compared to the final week of the trial. A repeated measures general linear model will be used to test differences between the two trial arms across baseline and the 10 end-of-week measurements of the LC-score and numLCsym.
- 3.5.5 Adherence to the Fasting intervention will be tracked for each participant using self-reported assessment of whether the components of the intervention were followed each week of the study and will be reported as percentages.
- 3.6.5 Adverse events and major adverse events will be recorded for each participant and reported as percentages along with counts of events at each time point.
- 3.7.5 Analyses will use R Studio.
- 3.8.5 Exploratory analyses will examine other features of the data set
- 3.9.5 Subgroup analyses may be conducted using non-paired two-sided t-tests to identify statistically significant correlations between mean percent decreases in the primary measures and various baseline characteristics.

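### SAP 3.6.5 reports adverse events by time point, with no split by treatment and no stated denominator, so the safety of fasting may be diluted or left unseparated

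*Combined protocol and SAP*

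**What the plan says.** SAP 3.6.5 (section 4.0, Analysis Plan) is the only statement on how adverse events are analysed: adverse and major adverse events are to be logged per participant and "reported as percentages along with counts of events at each time point". It mentions no treatment, period, sequence, denominator or Fasting-versus-TRE comparison.

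SAP 2.0 fixes the layout: "The trial population consists of 58 individuals, including 29 randomized to 4 weeks of once-per-week 23-60 hour water-only fasting" first, "and the other 29 randomized to 4 weeks of daily 10-12 hour TRE" first, and ten weeks in all, "including a 2-week run-in period of daily 10- to 12-hour TRE". Each sequence then has two four-week treatment periods.

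Events are collected weekly. Protocol Safety Procedures, step 25: "As subjects complete their weekly Symptom Surveys, REDCap notifications will check for self-reported Serious and Concerning Adverse Events". An event can therefore be placed in a study week and so under a treatment.

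Three provisions bear on the denominator:
- SAP 3.1.5 names intent-to-treat, then includes in the analyses those with symptom scores at each time point.
- Protocol Study Procedures, step 20: "If a subject misses a key survey, then they are considered withdrawn from the study". The survey that closes the four fasting weeks is one of the key surveys.
- Protocol Safety Procedures, step 24, allows a subject to be removed after a safety concern. Step 21 of Study Procedures keeps the records of removed subjects.

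**The concern.** In a two-sequence crossover, half the participants are on each treatment in any treatment week. A table indexed by study week, with sequences pooled, averages the treatments and does not contrast them. The protocol directs its specific safety procedures at the fasting component (calls before the first fast, reminders that fasting can be stopped, electrolytes). The SAP's power section says that, apart from two case reports, there is no prior study of fasting in Long COVID. The natural safety question is how often events occur on Fasting compared with TRE, and 3.6.5 does not commit to a table that answers it.

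The denominator is a second gap. If percentages rest on people who completed surveys, someone who left during a fasting period could be missing from the figures that describe fasting.

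**Working it through.** **Inputs.** Sequence sizes of 29 and 29, a common two-week run-in and eight treatment weeks come from SAP 2.0. The documents give no event rates, so those below are assumptions: TRE 2% to 10% and Fasting 5% to 40% per week.

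**The plan's own figure.** 29 + 29 = 58, as stated. The share on Fasting in any treatment week is 29/58 = 50%.

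**Reading 1: study week, sequences pooled.** Let pF and pT be the weekly event rates on Fasting and TRE. In every treatment week the pooled rate is

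(29 × pF + 29 × pT) / 58 = (pF + pT) / 2.

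- With pF = 20% and pT = 5%: (5.8 + 1.45) / 58 = 12.5%, in both periods. Period 1 minus period 2 is 0 for any pair of rates.
- The same 12.5% arises from 12.5% and 12.5%, from 25% and 0%, and from 5% and 20%. The pooled weekly figure does not identify the two rates.
- Everyone is on TRE during run-in. If the run-in rate equals pT, the rise from run-in to a treatment week is (pF + pT)/2 − pT = (pF − pT)/2, half the true difference. Across the assumed ranges:

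| TRE | Fasting | True difference | Rise over run-in |
|---|---|---|---|
| 2% | 5% | 3 points | 1.5 points |
| 5% | 20% | 15 points | 7.5 points |
| 2% | 40% | 38 points | 19 points |

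That rise is a before-and-after comparison, so it also carries any change over time.

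**Sensitivity to unequal sequences.** With 31 fasting first and 27 fasting second, and rates of 20% and 5%, period 1 gives (6.2 + 1.35)/58 = 13.0% and period 2 gives (5.4 + 1.55)/58 = 12.0%. The treatments are still not separated.

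**Reading 2: weeks aligned by treatment.** Each of the 58 contributes four weeks to Fasting and four to TRE. The table shows 20% against 5%, a difference of 15 points, and the problem in reading 1 disappears.

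**Denominator.** SAP 2.0 describes 58 people who all took part for ten weeks. Step 20 treats anyone who misses a key survey as withdrawn. If 3.6.5 inherits either the 58 or the 3.1.5 restriction, events in people who left during fasting need not enter the percentages. The documents give no count of such people, so this part has no computed size.

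**The case against.** The strongest reply is that 3.6.5 does not say the sequences are pooled, and the same section uses *time point* in a treatment-aligned sense. Item 3.3.5 has symptom scores "compared between the two study arms using the two-sided paired T-test at each time point", and a paired Fasting-versus-TRE test needs weeks matched by treatment. It goes on to the first three weeks within each treatment, and 3.4.5 lists the ends of Fasting and of TRE. This stands: a reader might infer that the planned table cannot show the safety of fasting, and the documents do not support that as an absolute. It does not settle the matter. Those items govern symptoms. Item 3.4.5 also uses a calendar series of ten weekly measurements and includes the end of the trial, when one sequence has just fasted and the other has not. Nor would adding *by arm* be enough, because the protocol synopsis uses the word for sequences and SAP 3.0 uses it for treatments.

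A reader might also infer that the table would look the same whether or not fasting causes events. It would not. With TRE held at 5% and run-in at the same rate, treatment weeks show 5% if fasting adds nothing and 12.5% if the Fasting rate is 20%. The signal is diluted and confounded with time, but it is present.

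On withdrawals, step 20 concerns missed surveys and does not mention adverse events; records are kept, and event forms are created within 24 hours. No text says that withdrawn people's events are left out. This stands too, so the denominator point is conditional.

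Finally, safety is not an aim, hypothesis or endpoint, 3.6.5 is descriptive, and individual events receive medical review. The absence of a confidence interval is therefore not an error.

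**Conclusion.** The point holds as underspecified adverse event reporting with a real consequence under a reading the SAP leaves open. If *time point* means study week with sequences pooled, the two treatment rates cannot be separated, and an excess on Fasting appears at half its size over run-in, mixed with time effects. The halving rests on the 29/29 split and on a run-in rate equal to the TRE rate; the event rates are illustrative. Under a treatment-aligned reading this part of the problem is absent.

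The denominator is unstated under either reading. People withdrawn during fasting could drop out of the percentages, but the documents neither say that they do nor how many there were. The synopsis gives a sample size of 96 and the SAP describes 58; a reader might take the gap as the number lost after randomisation, but neither document says so.

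**What to change.** Replace the by-time-point rule in SAP 3.6.5 with a table of adverse and major adverse events by treatment at onset (run-in, TRE, Fasting), giving participants with any event and counts of events. Show the same table by period or by sequence. Use as denominator everyone who started the period concerned, including those who later withdrew, and state that the 3.1.5 restriction to people with symptom scores does not apply to safety. If a weekly display is kept, define *time point* as week within treatment.

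A Fasting-minus-TRE difference in participants with any event, with a 95% confidence interval that respects the pairing, is a useful optional addition.

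The cost is SAP wording and one table. Weekly collection and the retained records of removed subjects mean that no new data are needed.

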2.1 Trial Endpoints

2.1.5 **Primary endpoint**: The primary trial endpoints are: 1) a composite of symptom severity scores for 28 common Long COVID symptoms and 32 less common symptoms, and 2) a sum of the presence or absence of the 60 symptoms.

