2.1 Power Calculation

2.1.5 As no prior study involving fasting and Long COVID exist, with the exception of two case reports, this trial's sample size was estimated based on the 2022 understanding of Long COVID and on publications at that time about Long COVID that had a nascent understand of the symptoms involved in the condition. The expected effect of fasting on Long COVID symptoms was estimated roughly to require 40 to 90 individuals per trial arm, in part depending on the severity of Long COVID symptoms experienced by those who would enroll.

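### SAP item 3.9.5 allows an unlisted set of subgroup t-tests aimed at finding significance, with no error control and no exploratory label; the false-positive rate is uncontrolled and cannot be determined from the documents

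*Combined protocol and SAP*

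**What the plan says.** The rule is in the SAP, section 4.0, 3.1 Analysis Plan, item 3.9.5: "Subgroup analyses may be conducted using non-paired two-sided t-tests", and the stated purpose is "to identify statistically significant correlations between mean percent decreases in the primary measures and various baseline characteristics". The wording is permissive, so the analyses are optional.

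The related text is as follows.

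- **Primary measures.** SAP section 3.0, 2.1 Trial Endpoints, names two: a severity composite over 60 symptoms and "2) a sum of the presence or absence of the 60 symptoms".
- **Exploratory label.** Item 3.8.5 reads "Exploratory analyses will examine other features of the data set". It stands beside 3.9.5 and does not contain it.
- **Baseline variables.** Item 3.2.5 says "Demographics, anthropometric variables, risk factors, COVID-19 vaccinations, other medications, and socioeconomic variables will be described" and goes on to summary statistics. It is a descriptive list and is not linked to 3.9.5.
- **Not stated anywhere.** The documents give no alpha, multiplicity adjustment, testing order, list of subgroup characteristics or cut-points. The Limitations section mentions the limited sample size but not multiple testing.

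**The concern.** The declared purpose of 3.9.5 is to find which characteristics reach significance, not to estimate how response varies. The set is open and each characteristic can be tested on two measures, so the number of tests is unlimited. If several are run at a nominal level, a chance result becomes much more likely than that level suggests, and a reader could take it as evidence about who benefits from fasting. Because the analyses are optional and the characteristics unnamed, which ones to run can be decided after the data are seen. This adds flexibility.

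There is a second, smaller issue. A two-group t-test can handle a continuous characteristic, such as age or BMI if examined, only after it is split. Splitting discards information, and the SAP fixes no cut-point.

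**Working it through.** The plan states no error rate or test count, so there is no figure to reproduce. The check asks what the rate would be for a range of counts.

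**Inputs from the SAP.** There are two primary measures (2.1 Trial Endpoints). The test is a two-sided unpaired t-test (3.9.5). For the analysed number, section 2.0 says "The trial population consists of 58 individuals".

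**Assumptions.** Alpha is two-sided 0.05. The number of characteristics K is 3, 6, 10 or 15. The correlation between the two measures is between 0 and 0.9, and among characteristics between 0 and 0.5. None of these is in the documents.

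**Step 1: independent tests (upper reference).** With 2K tests, the chance of at least one false positive is 1 − 0.95^(2K), and the expected number of false positives is 2K × 0.05.

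- K = 3: 1 − 0.95^6 = 26%; expected 0.3
- K = 6: 1 − 0.95^12 = 46%; expected 0.6
- K = 10: 1 − 0.95^20 = 64%; expected 1.0
- K = 15: 1 − 0.95^30 = 79%; expected 1.5

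The rate reaches 50% at ln 0.5 / ln 0.95 = 13.5 tests, that is, about 7 characteristics on two measures.

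**Step 2: correlated tests.** This is a null simulation with n = 58, each characteristic dichotomised near the middle, two measures, and t-tests at 0.05.

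| K | Measures correlated 0.8, characteristics independent | Measures correlated 0.9, characteristics independent | Lowest simulated |
|---|---|---|---|
| 3 | 21% | 19% | 19% |
| 6 | 39% | 36% | 33% |
| 10 | 57% | 51% | 46% |
| 15 | 71% | 67% | 56% |

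For K = 6, 10 and 15, the lowest values come from runs that also let the characteristics correlate up to 0.5. Both measures are built from the same 60 symptoms, so strong positive correlation is likely and the lower part of each range is more plausible. With measures correlated 0.8 to 0.9, the rate reaches 50% at roughly 8 to 10 characteristics or slightly more.

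**Step 3: effect of adjustment.** With K = 6 there are 12 tests, and Bonferroni uses 0.05/12 = 0.0042 per test. If the tests are independent, the family-wise rate is 1 − (1 − 0.0042)^12 = 4.9%, and positive correlation lowers it. Holm controls the same rate and is never less powerful.

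**Step 4: cost of splitting a continuous characteristic.** Take a true correlation of 0.35 and n = 58, with the Fisher approximation for one test at 0.05.

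- Continuous: atanh(0.35) × √55 = 0.365 × 7.42 = 2.71; 2.71 − 1.96 = 0.75; power about 77% (simulation 78%).
- Median split: the correlation shrinks by √(2/π) = 0.798 to 0.279; atanh(0.279) × √55 = 2.13; 2.13 − 1.96 = 0.17; power about 57% (simulation 57%).

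**The case against.** The strongest defence is that this is a supplementary item with little weight. It is optional. No aim, hypothesis or endpoint in the SAP concerns predictors of response. It comes last in the analysis plan, directly after the exploratory item, and many readers would treat it as exploratory anyway. All of this stands and keeps the severity low. It does not remove the point, because the wording of 3.9.5 seeks significance and carries no label.

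Stronger readings are tempting, but the documents do not support them.

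- **A false finding is about as likely as not.** A reader might infer this, but it requires alpha of 0.05 and about 7 characteristics if the tests are independent, or about 8 to 10 if the two measures are strongly correlated. The SAP gives neither figure.
- **Item 3.2.5 sets the family at six classes.** That item is descriptive and not tied to 3.9.5, so K = 6 is only an illustration.
- **Every characteristic that crosses the threshold will be reported as a predictor.** The SAP has no such reporting rule.
- **Cut-points will be chosen from the data.** In simulation, taking the best of tertile or median cuts raises the error for one covariate on one measure from 5% to about 12%, and scanning all cuts raises it to 29%. The SAP describes no such procedure, and binary characteristics such as sex need no cut.
- **The small sample inflates the error.** A valid t-test holds its level at any sample size. The family-wise rate depends on the number and correlation of the tests, not on there being 58 participants.

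**Conclusion.** The point holds in limited form. Item 3.9.5 permits an open family of significance-seeking subgroup tests on two measures, with no error control and no exploratory label. The family-wise false-positive rate is uncontrolled and the documents do not allow it to be determined. At an assumed two-sided 0.05 it is about 19 to 26% for 3 characteristics, 33 to 46% for 6, 46 to 64% for 10 and 56 to 79% for 15, with the lower ends more plausible. Even 3 characteristics give about four to five times the per-test level (19/5 = 3.8; 26/5 = 5.2). Splitting any continuous characteristic would also lose power, from 78% to 57% in the example, and leave the cut-point open.

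The primary comparison is not affected. Severity is minor, and the change is a cheap improvement.

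**What to change.** Reword item 3.9.5 as follows.

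1. Call the subgroup analyses exploratory and hypothesis-generating, and delete the clause that gives finding significance as their purpose.
2. Report an estimate with a 95% confidence interval for every characteristic examined, and state how many were examined.
3. Analyse continuous characteristics by regression on their original scale, without splitting.
4. If a p-value is used to name a predictor, adjust over all characteristics and both primary measures, by Holm or at a 5% false discovery rate.

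The cost is SAP wording and a few lines of analysis code, with no new data. The downside is that no single subgroup result can be claimed as established.
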